#### **1.4.2 Interference with oral P2Y12 receptor antagonists**

Co-administration of the oral, irreversible P2Y12 receptor antagonists clopidogrel and prasugrel during infusion of cangrelor is prohibited given the potential lack of clopidogrel- / prasugrel-mediated IPA [Kengrexal® SmPC]. Mechanistically, this is due to the short half-life of the active metabolites of clopidogrel and prasugrel that, while still in the circulation, cannot bind to the receptor which is pre-occupied by cangrelor. Instead, if administered immediately after stopping the cangrelor infusion, clopidogrel and prasugrel both exhibit their expected PD effects [Steinhubl 2008, Schneider 2014, Judge 2016, Rollimi 2016].

*In vitro* studies have been conducted to assess the PD interaction potential of ACT-246475 with ticagrelor and the active metabolite of prasugrel (P-AM) [B-16.064]. Here, additive effects were determined when ACT-246475 was added to platelets pre-bound to ticagrelor or P-AM. Instead, if P-AM was added to platelets pre-bound to ACT-246475 the inhibitory effects of P-AM on platelet aggregation were reduced.

Because of the current ESC guidelines [Valgimigli 2018] recommending administration of a loading dose of oral P2Y12 receptor antagonist as early as possible after diagnosis of an AMI, it is expected that many subjects participating in the study will receive an oral P2Y12 antagonist.

In the absence of clinical data regarding administration of the irreversible P2Y12 antagonists clopidogrel or prasugrel following administration of ACT-246475, if oral treatment with a P2Y12 receptor antagonist is to be initiated in subjects participating in this study, a reversible P2Y12 receptor antagonist (e.g., ticagrelor) must be used.

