#### Conditions associated with the qualifying AMI:

- 1) Cardiogenic shock or severe hemodynamic instability (e.g., Killip class 3–4).
- 2) Cardiopulmonary resuscitation.
- 3) Loading dose of any oral P2Y12 receptor antagonist prior to randomization.

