### **5.2.2 Reporting of previous/concomitant therapy**

The use of all study-concomitant therapy (including traditional and alternative medicines, e.g., plant-, animal-, or mineral-based medicines) will be recorded in the eCRF.

Previous therapies related to treatment and prevention of CAD will be recorded in the eCRF if discontinued less than 1 month ( $\leq 30$  days) prior to providing informed consent. Previous therapies related to treatment of the study-qualifying AMI will be recorded in the eCRF.

The generic name, start/end dates of administration (as well as whether it was ongoing at administration of study treatment and/or EOS), route, dose, and indication will be recorded in the eCRF. In addition, for oral P2Y12 receptor antagonists, the time of each administration during the study will be recorded in the eCRF.

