### **5.2.3 Allowed concomitant therapy**

Standard treatment of AMI is allowed including anticoagulants and oral P2Y12 receptor antagonists.

When initiation of an oral P2Y12 receptor antagonist is considered for a subject [see also Section 1.4.2], it must be initiated after administration of ACT-246475. In absence of clinical data regarding administration of an irreversible P2Y12 antagonist following the administration of ACT-246475, it is requested to use a reversible oral P2Y12 receptor antagonist (e.g., ticagrelor).

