6.8.1.2 Analysis

The analyses described in this section consider the primary endpoint, i.e., PD response. Sensitivity analysis of the PD endpoints will be described in Section 6.8.1.3.

Unless stated otherwise, all analyses will be conducted on the mFAS.

Hypotheses and statistical model

The primary objective is to assess IPA 30 min after a single s.c. injection of ACT-246475 in subjects with AMI receiving conventional antithrombotic treatment (e.g., aspirin, oral P2Y₁₂ receptor antagonists, anticoagulants).

To achieve this objective, the testing strategy will be to test the study treatment effect (using the proportion *p* of responders, i.e., achieving PRU < 100 at 30 minutes post-injection) for each of the two doses, considering the following hypotheses:

$$H_{0HD}: p_{HD} \leq 50\% \text{ vs } H_{1HD}: p_{HD} \geq 85\%$$

$$H_{0LD}: p_{LD} \leq 50\% \text{ vs } H_{1LD}: p_{LD} \geq 85\%$$

where LD is the lower ACT-246475 dose (8 mg), and HD the higher ACT-246475 dose (16 mg).

Each of the two null hypotheses will be tested by a two-sided z-test at a significance level (alpha) of 0.025, which is an overall level of 0.05 for the study level and adjusted for multiplicity using Bonferroni method.

Main analysis

The primary statistical analysis will be performed on the mFAS population for each dose level.

It will be based on the study treatment received (which may differ from the assigned one).

The analysis of the primary endpoint will be performed for each of the two doses independently, i.e., considering 2 null hypotheses (proportion of patients achieving a

response is less than or equal to 50%) at 0.025 type I error each [see protocol section 10.3.3.1].

The study will be declared positive for the primary objective, if at least 1 out of the 2 null hypotheses is rejected at 0.025 type I error level.

A one-sided z-test will be computed and the 95% CI of the proportion of responders will be provided.

A summary of response, in terms of number (%) of responding subjects, will be provided.

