6.8.2.2 Analyses

Summary statistics will be provided for the PD endpoint variable *PRU_{60m} status*, and individual data will be listed. It will be analyzed similarly to the primary PD endpoint in Section 6.8.1.2, and will use the same factors.

A longitudinal analysis of the study treatment effect, on *PD profile over time* will be performed using a mixed model with PRU as the dependent variable, subject as a random factor, and study treatment (ACT-246475 8 mg, and ACT-246475 16 mg), PRU level at baseline, time from onset of symptoms to study treatment administration (continuous, hours), age (continuous), sex (male, female), and assessment time (15, 30 and 60 minutes) as fixed factors.

The proportion of subjects with PRU < 100 by assessment time (0 to 60 minutes) will be plotted as bar charts.

Descriptive statistics of PRU relative change from baseline at each time point will be provided, where change from baseline is defined as the ratio of $([PRU \text{ at time } t - PRU \text{ pre-dose}] / PRU \text{ pre-dose})$ expressed in percentage.

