Appendix B Protocol deviation list

The actual list of protocol deviations leading to exclusion from analysis set will be updated prior to study closure if required.

The table below provides the reasons considered for excluding subjects from analysis set.

Table 4 Definition of exclusions from analysis sets

Reason for exclusion from set	Reason	Programmable condition
Screened set	Informed consent not initially obtained for the study	no record in DS where DS.DSDECOD='INFORMED CONSENT OBTAINED' or DS.DSSTDTC='' when DS.DSDECOD='INFORMED CONSENT OBTAINED'
Randomized set	Not randomized	no DS.RANDNO
Full Analysis set	Subject did not get study treatment	EX.EXDOSE not >0
Modified FAS	30-minute post-dose VerifyNow [®] blood sample missing	missing LB.LBSTRESN where LB.LBTESTCD= P2Y12RU and LB.LBTPT= 30 MINUTE POST DOSE
Safety Set	Subject did not get study treatment	EX.EXDOSE not >0
Per Protocol set	Subject included without a type 1 MI	MH.MHLLT='Acute myocardial infarction type 2' (LLTCD=10079263) where MH.MHENRTPT='ONGOING' and MH.MHENTPT='INFORMED CONSENT' or at least one record with IE.IETESTCD = INCL04
Per Protocol set	Onset of AMI symptoms more than 6 hours prior to randomization	at least one record with IE.IETESTCD = INCL03
Per Protocol set	Subject included with severe hemodynamic instability	at least one record with IE.IETESTCD = EXCL01
Per Protocol set	Subject received a loading dose of oral P2Y ₁₂ receptor antagonist prior to randomization	at least one record with IE.IETESTCD = EXCL03
Per Protocol set	Subject with concomitant important anemia	at least one record with IE.IETESTCD = EXCL05

Per Protocol set	Subject with concomitant platelet disorders	at least one record with IE.IETESTCD = EXCL08
Per Protocol set	Subject with concomitant disease or condition that may have prevented subject from complaining with study requirements of may be a confounder of study interpretation.	at least one record with IE.IETESTCD in(EXCL12, EXCL14, EXCL15)
Per Protocol set	Incorrect administration of the study drug	DV.DVREFID = 02C01, 02C02
Per Protocol set	30-minute post-dose VerifyNow® blood sample collected outside of the protocol-defined window	DV.DVREFID = 03F03 or computed as need be
Per Protocol set	Issues with blood sample collection or processing for platelet aggregation assays	DV.DVREFID = 03F10, 03F08
Per Protocol set	Treatment with forbidden i.v. platelet inhibitors before assessment of the 30-minute time point.	DV.DVREFID = 04A02

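### The per-protocol set does not exclude oral P2Y12 loading between randomisation and injection, or forbidden oral platelet inhibitors before the 30-minute sample

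*SAP*

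**What the plan says.** The protocol has three rules on oral P2Y12 antagonists.

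- Section 4.4, criterion 3, excludes a loading dose of any oral P2Y12 "receptor antagonist prior to randomization".
- Section 5.2.3 allows an oral agent as standard care, but "it must be initiated after administration of ACT-246475".
- Section 5.2.4 forbids clopidogrel and prasugrel, along with cangrelor and glycoprotein IIb/IIIa inhibitors, from screening to the last PK sample.

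Section 1.4.2 says of oral use that "it is expected that many subjects participating in the study will receive an oral" P2Y12 antagonist. Section 5.2.2 adds that for these drugs "the time of each administration during the study will be recorded in the eCRF".

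SAP Table 4 carries this into the PPS with two rows. One is eligibility record EXCL03, a loading dose before randomisation. The other is "Treatment with forbidden i.v. platelet inhibitors before assessment of the 30-minute time point".

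Under SAP 6.8.1.3 the main analysis of the 30-minute response and of the first-hour response is repeated on the PPS if that set is at least 10% smaller than the mFAS. The 60-minute status and the PRU-over-time model use the FAS (SAP 6.8.2). Of the 60-minute status SAP 6.8.2.2 says "It will be analyzed similarly to the primary PD endpoint in Section 6.8.1.2", and SAP 6.8.2.3 plans no sensitivity analysis for it.

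**The concern.** The PPS is meant to hold subjects without major deviations that affect the treatment effect (SAP 4.1.5). The i.v. row shows that the SAP regards another platelet inhibitor before the 30-minute reading as such a deviation. It leaves out the oral agents that the protocol restricts for the same period.

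Protocol 1.4.2 makes the pre-injection case plausible: in vitro, ACT-246475 had additive effects on platelets already bound by ticagrelor or by prasugrel's active metabolite. The interval is not empty, because the kit is taken and prepared after randomisation, and preparation restarts with a new kit if it goes wrong (5.1.3.2, 5.1.4).

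Each dose is tested against a fixed 50% with no control arm. A response helped by an oral agent cannot be recognised from the response rate alone. If the sensitivity set keeps these subjects, agreement between PPS and mFAS gives no reassurance on this point. No planned analysis relates the recorded oral dose times to PRU.

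**Working it through.** **1. Rules against Table 4**

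| Subject | Protocol rule broken | Row in Table 4 | In PPS? |
|---|---|---|---|
| Oral load before randomisation | 4.4, criterion 3 | EXCL03 | No |
| Oral load after randomisation, before injection | 5.2.3 | none | Yes |
| Clopidogrel or prasugrel after randomisation, before 30-min sample | 5.2.4 | none | Yes |
| Forbidden i.v. inhibitor before 30-min sample | 5.2.4 | i.v. row | No |
| Permitted oral agent after injection | none | none needed | Yes, as intended |

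The second and third lines are the gap. The row for incorrect administration (codes 02C01, 02C02) concerns the study drug by its label. The codes themselves are not defined in the documents.

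**2. The plan's sample size**

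Inputs from protocol 10.5: null 50%, alternative 85%, power 90%, alpha 0.025 per dose. For a one-sample z-test with the null variance and two-sided 0.025:

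n = [(2.2414 × √(0.5 × 0.5) + 1.2816 × √(0.85 × 0.15)) / 0.35]² = [(1.1207 + 0.4576) / 0.35]² = 20.34, rounded up to 21. Power at 21 is 91.2%. The stated 21 per arm reproduces.

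**3. Responders needed**

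z = (x/21 − 0.5) / √(0.25/21). This gives 1.53 at x = 14, 1.96 at 15 and 2.40 at 16. SAP 6.8.1.2 describes the test in two ways: "Each of the two null hypotheses will be tested by a two-sided z-test at a significance level (alpha) of 0.025" and "A one-sided z-test will be computed and the 95% CI of the proportion of responders will be provided". Two-sided 0.025 (critical value 2.24) needs 16 of 21. One-sided 0.025 (1.96) needs 15 of 21. Both are carried below. One responder is 1/21 = 4.8 percentage points.

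**4. Sensitivity of an arm of 21 (assumptions, not estimates)**

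Let the true ACT-246475 response be 50%.

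Upper bound: k subjects are certain responders through the oral drug. P(success) = P(X ≥ r − k), with X ~ Bin(21 − k, 0.5).

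| k | r = 15 | r = 16 |
|---|---|---|
| 0 | 3.9% | 1.3% |
| 2 | 8.4% | 3.2% |
| 3 | 11.9% | 4.8% |
| 6 | 30.4% | 15.1% |

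Alternative: the oral agent converts a share q of those who would not otherwise respond, so the response rate is 0.5 + 0.5q and X ~ Bin(21, 0.5 + 0.5q).

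| q | r = 15 | r = 16 |
|---|---|---|
| 0 | 3.9% | 1.3% |
| 5% | 6.3% | 2.3% |
| 10% | 9.6% | 3.9% |
| 20% | 20.0% | 9.6% |

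The documents give neither k nor q. Both tables use the full 21 per arm; a PPS arm could be smaller.

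**5. When the PPS analysis runs**

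Taking an mFAS of 42, 4 exclusions are 4/42 = 9.5% and 5 are 5/42 = 11.9%. At least 5 exclusions are needed. Missing exclusion rows therefore also make it less likely that the PPS analysis is run at all.

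**The case against.** The strongest reply is that oral treatment belongs to the question. The primary objective concerns subjects on conventional antithrombotics, oral P2Y12 antagonists included, and 5.2.3 permits oral loading after injection. Keeping those subjects follows the objective. This stands, and nothing here asks for their removal.

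The effect at 30 minutes may also be small. Protocol 1.4.5 describes delayed absorption and onset of oral agents in ACS. Section 1.4.2 reports that prasugrel's active metabolite had less effect in vitro on platelets already bound by ACT-246475. This also stands. It weakens the case of a forbidden oral agent given after injection, but does not settle a load given before it.

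Pre-injection oral use is not hidden. SAP 5.4.6 tabulates oral P2Y12 antagonists at baseline, and SAP 10.7 ties that term to study drug administration. The table would show such use, mixed with maintenance treatment, but excludes nobody and is not linked to response.

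Finally, Appendix B lets the deviation list be updated before study closure, and the general PPS wording could admit a pre-injection load. That is true, but in an open-label trial an exclusion added late carries less weight than one fixed in advance.

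**Conclusion.** The gap holds and is narrow. Two kinds of protocol departure that bear on the 30-minute reading are missing from Table 4, so the PPS analyses of the 30-minute and first-hour responses keep those subjects. The primary mFAS test is not put in question.

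A reader might go further and infer that oral loading effects are credited to ACT-246475 in every 30- and 60-minute analysis, the PPS included. The documents do not support that. Loading after injection is permitted and within the objective. The 60-minute status and the PRU-over-time model are not run on the PPS; the 60-minute value reaches it only through the first-hour response. The expectation that many subjects will receive an oral agent says nothing about how many do so before the 30-minute sample.

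The size of any bias is unknown. With delayed oral onset it is likely smaller at 30 than at 60 minutes. The k figures are an upper-bound illustration: they treat k subjects as certain responders, although under the same 50% assumption half would have responded anyway.

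**What to change.** 1. In SAP Table 4, keep the EXCL03 row and add a PPS exclusion for any oral P2Y12 loading dose with a recorded time before the ACT-246475 injection. Extend the i.v. row to every platelet inhibitor forbidden by protocol 5.2.4, oral or i.v., given within its prohibited period and before the 30-minute sample.

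2. Add a descriptive, supportive display by dose group: response at 30 and at 60 minutes (n, %, CI) for subjects with and without an oral P2Y12 dose before that sample, from the recorded dose times.

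Leave the primary analysis and its test as they are, with permitted post-injection loading included. Do not add an oral-dose indicator to the mixed model: it would be a post-dose covariate, confounded by the reasons for early loading.

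The cost is SAP wording, two programmed conditions and two small tables, with no new data collection. The split groups will be small and are not randomised, and one may be nearly empty, so the display can describe but not test.

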## 5.2.4 Forbidden concomitant therapy

The following medications are prohibited from screening and up to the last PK blood collection:

- Fibrinolytic therapy (e.g., streptokinase, alteplase...).
- OATP1B1 and OATP1B3 inhibitors (e.g., atazanavir, ritonavir, lopinavir, simeprevir, clarithromycin, erythromycin, cyclosporine, eltrombopag, lapatinib, gemfibrozil, rifampin)
- Glycoprotein IIb/IIIa inhibitors.
- Irreversible oral P2Y12 antagonists (clopidogrel or prasugrel)
- Cangrelor

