### **10.5 Sample size**

The computation of the sample size was performed using East 6.0 software (version 6.4.0.1, 30 August 2016) from Cytel Inc.

The sample size is based on the study primary objective of assessing IPA 30 min after ACT-246475 administration, as assessed by the proportion of subjects achieving a response (i.e., PRU < 100 at 30 min post study drug administration). The sample size should be sufficient to allow the rejection at least one of the null hypotheses.

The study should include 21 subjects evaluable for the primary PD endpoint in each arm considering:

- an overall two-sided type I error of 0.05, adjusted for multiplicity using the Bonferroni method for each of the 2 null hypotheses (testing each dose at an alpha level of 0.025),
- a power of 90%, and
- the following assumptions for the response rate under the null and alternative hypotheses as reported in the table below.

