6.8.1.1 Variable

The primary pharmacodynamic (PD) endpoint is the *PD response* that is defined for each subject as a PRU < 100 at 30 min after study drug injection, as measured via VerifyNow[®].

The primary PD variable (PRU_{30m}) is the platelet reactivity as measured by VerifyNow[®] at 30 min after study drug injection [see the table of assessments in the protocol, table 2].

The analysis variable of the PD response is defined as follows for a given subject:

$$\begin{aligned} & \text{IF } PRU_{30m} < 100 \\ & \text{THEN } PD \text{ response} = \text{YES} \\ & \text{ELSE } PD \text{ response} = \text{NO} \end{aligned}$$

PRU time is based on planned time point and not on the actual collection time.

Supportive primary PD endpoint

The following endpoint is not described in the protocol and has been added. The main purpose is to assess the effect of the two study treatment doses, when relaxing the time of a PRU < 100, i.e., considering as a response a PRU < 100 at 15, 30 or 60 min. post injection.

This endpoint is defined as per the following algorithm and will describe the subject's *PD response within the 1st hour*:

*IF minimum of (PRU_{15m}, PRU_{30m}, PRU_{60m}) < 100
THEN PD response within 1st hour = YES
ELSE PD response within 1st hour = NO*

Where PRU_{15m}, PRU_{30m}, and PRU_{60m} refer to PRU measured by VerifyNow® at 15, 30, and 60 minutes after study drug administration.

PRU time is based on planned time point and not on the actual collection time.

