6.8.1.3 Supportive/sensitivity analyses

IPA as measured by VerifyNow® will also be summarized as a continuous variable.

Those summaries will be provided considering the available PD assessment time points (baseline, 15, 30, and 60 min post dose).

A mixed model to assess treatment effect at 30 min. from start of treatment injection on platelet reactivity as measured by VerifyNow®, i.e., PRU value, will be performed using subject as a random factor, and treatment (8 mg, and 16 mg), age (continuous), sex (male, female), and time from onset of symptoms to study treatment administration (continuous, hours), as fixed factors.

Assuming relevant number of subjects (i.e., ≥ 10 subjects) in each STEMI/NSTEMI subgroup, the consistency across STEMI and NSTEMI subgroups will be assessed by testing the interaction effect of STEMI/NSTEMI with study treatment dose in the primary endpoint analysis. Logistic regression analysis of the PD response will be performed using ACT-246475 dose (8 mg vs 16 mg), ST-segment elevation (STEMI vs NSTEMI), age (continuous), and gender (male vs female) as covariates.

The same analysis as described in the main analysis section will be performed on the additional PD response within the 1st hour endpoint using the FAS.

The main analysis, on the PD response, and PD response within the 1st hour, will be repeated on the PPS if the PPS is at least 10% smaller than the mFAS.

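### The per-protocol rules stop at the 30-minute sample, yet the same set is used for the first-hour response, so a forbidden i.v. inhibitor or an off-window draw can create a per-protocol responder

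*SAP*

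**What the plan says.** SAP 6.8.1.3 states: "The main analysis, on the PD response, and PD response within the 1st hour, will be repeated on the PPS". This happens only if the PPS falls short of the mFAS by 10% or more. SAP 6.8.1.1 adds the first-hour endpoint, "considering as a response a PRU < 100 at 15, 30 or 60 min. post injection", and derives it as the minimum of the three values. The same section assigns each reading to its planned time point, whatever the actual draw time.

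Appendix B, Table 4 defines one PPS. Three of its rows bear on the validity of a PRU reading:

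| Row in Table 4 | Time point named |
|---|---|
| Sample outside the protocol window (03F03) | 30 minutes only |
| "Issues with blood sample collection or processing for platelet aggregation assays" (03F10, 03F08) | none |
| "Treatment with forbidden i.v. platelet inhibitors before assessment of the 30-minute time point" (04A02) | up to 30 minutes only |

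The protocol is wider on both counts. Section 5.2.4 says: "The following medications are prohibited from screening and up to the last PK blood collection"; the list includes glycoprotein IIb/IIIa inhibitors and cangrelor. Protocol Table 2 sets ±5 min at 15, 30 and 60 minutes alike. SAP 6.8.3 plans no imputation and has no rule that sets aside a single invalid reading.

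**The concern.** A per-protocol analysis is meant to show the result without deviations that could distort it. For the first-hour response, Table 4 does not do that between the 30- and 60-minute samples. A forbidden platelet inhibitor given in that interval is a protocol deviation, and its effect on PRU would be credited to ACT-246475. The setting makes this conceivable: subjects are scheduled for an invasive strategy, and Protocol Table 2 allows for a procedure within 8 h of dosing.

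A second, softer issue runs the other way. The sample-fault row names no time point. Read literally, a spoiled pre-dose, 15- or 60-minute tube would remove a subject whose 30-minute PRU is sound.

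SAP 11.1.1 drops the FAS sensitivity analysis of the 30-minute response, so the PPS is the only alternative analysis set left for that endpoint.

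**Working it through.** **1. The plan's own figure.** Protocol 10.5 and Table 4 give 50% versus 85%, alpha 0.025 per dose, 90% power and 21 per arm. With the null-variance one-sample z-test,

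n = [(z_α·√(0.5·0.5) + z_power·√(0.85·0.15)) / 0.35]².

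- Two-sided 0.025: [(2.2414·0.5 + 1.2816·0.3571)/0.35]² = 20.34, so 21. This reproduces.
- One-sided 0.025: [(1.9600·0.5 + 1.2816·0.3571)/0.35]² = 16.87, so 17. This does not.

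SAP 6.8.1.2 states both "Each of the two null hypotheses will be tested by a two-sided z-test at a significance level (alpha) of 0.025" and "A one-sided z-test will be computed and the 95% CI of the proportion of responders will be provided". I use the two-sided version because it gives the planned 21. Its pass mark is 16/21: z = (16/21 − 0.5)/√(0.25/21) = 2.40, against 1.96 for 15/21 and a critical value of 2.24.

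**2. Tracing subjects through Table 4.**

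- *I.v. inhibitor.* PRU is at or above 100 at 15 and 30 minutes, a forbidden inhibitor starts at, say, 40 minutes, and PRU is below 100 at 60 minutes. The i.v. row does not apply, because the drug came after the 30-minute assessment. The subject stays in, and the minimum makes a responder.
- *Off-window draw.* The 15- or 60-minute sample misses its window. The window row does not apply, and planned-time labelling keeps the value. A late 60-minute draw matters most, because it may fall outside the first hour altogether. A late 15-minute draw can still lie within the hour.
- *Direction.* With a minimum, one falsely low value settles the response and no valid high value can reverse it. The error can only raise the rate.

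**3. Possible size for the first-hour response.** The documents give no rate for such events, so this is an assumption. Let k subjects in an arm be false responders and let the rest respond at 50%. Then P(pass) = P(Binomial(21 − k, 0.5) ≥ 16 − k).

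| k | Arm of 21, pass mark 16 | Arm of 18, pass mark 14 |
|---|---|---|
| 0 | 1.3% | 1.5% |
| 1 | 2.1% | 2.5% |
| 2 | 3.2% | 3.8% |
| 3 | 4.8% | 5.9% |

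The arm of 18 is shown because the PPS analysis runs only when the set has shrunk. With 42 in the mFAS it needs 5 exclusions (5/42 = 11.9%; 4/42 = 9.5% is too few), which leaves 37. The second column is P(Binomial(18 − k, 0.5) ≥ 14 − k); for k = 3 it is (1365 + 455 + 105 + 15 + 1)/32768 = 5.9%. In an arm of 21, each false responder adds 1/21 = 4.8 points to the observed rate.

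**4. The sample-fault row.** Assume a fault probability q per sample, independent across samples. The chance of a sound 30-minute sample with a fault elsewhere is (1 − q)·(1 − (1 − q)²) counting 15 and 60 minutes, or (1 − q)·(1 − (1 − q)³) with pre-dose added.

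| q | Expected of 42 (15/60 min; with pre-dose) | Chance these alone reach 5 of 42 |
|---|---|---|
| 2% | 1.6; 2.4 | 2%; 9% |
| 5% | 3.9; 5.7 | 35%; 69% |

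These figures apply only if the row is programmed to cover all time points.

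**The case against.** **Building the PPS around 30 minutes was deliberate.** SAP 11.3 re-based it on the mFAS because that set serves the primary endpoint. The first-hour response is supportive, called exploratory in SAP 6.8.3, and is analysed first on the FAS. This stands as to weight. It does not close the gap, because SAP 6.8.1.3 itself sends the first-hour response to the PPS.

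**Table 4 may still be updated before study closure.** True. That is the route for a correction, but nothing commits to making this one.

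**Codes 03F08 and 03F10 are not defined in the documents.** SAP 4.1.5 speaks of major deviations that affect the treatment effect, and a faulty 60-minute tube does not affect a 30-minute responder rate. This stands: the second issue is an ambiguity in wording.

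Three stronger readings are tempting and are not supported:

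- *Every bad 60-minute reading stays in.* The sample-fault row as worded would already remove a subject with a faulty 60-minute sample. The gap concerns i.v. inhibitors after 30 minutes and off-window draws.
- *Subjects with a valid 30-minute PRU will be dropped.* The wording permits it, but undefined codes cannot establish it.
- *The PPS will lose much of its size and power.* At q = 5%, a row covering four samples removes 1 − 0.95⁴ = 18.5% of subjects, or about 17 left per arm. A row limited to 30 minutes still removes 5%, leaving about 20. Exact power at 85% is 75.6% at 17, 87.9% at 18 and 83.0% at 20, so the loss depends on where n falls on a saw-tooth. No fault rate or PPS power target is given, and needless exclusions would only make an extra analysis more likely to run.

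**Conclusion.** The point holds and should be corrected, as a limited one. As written, Table 4 lets a subject count as a per-protocol first-hour responder on a reading taken after a forbidden i.v. inhibitor or outside its window, and the resulting error favours the drug. With 1 to 3 such subjects in an arm of 21, the chance of reaching the pass mark at a 50% rate moves from 1.3% to between 2.1% and 4.8%. Those counts are assumed, and the calculation uses the two-sided reading of the test. The sample-fault row needs a stated time point; whether it would remove valid 30-minute data cannot be settled from the documents.

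A reader might infer that the main result is at risk. It is not: the primary analysis uses the mFAS and the 30-minute reading, and the success criterion depends on that alone. Only a conditional sensitivity analysis is affected.

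**What to change.** Make the assay-related PPS rules specific to the endpoint before database lock, leaving the eligibility and study-drug administration rows as they are.

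- **First-hour response on the PPS:** set to missing any 15-, 30- or 60-minute reading that is outside its ±5 min window, has a collection or processing fault, or was drawn after a forbidden i.v. platelet inhibitor was started. Derive the response from the remaining valid readings. Exclude the subject only if none remains.
- **30-minute response on the PPS:** limit the 03F08/03F10 row to the 30-minute sample, and say what the two codes cover.

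The cost is SAP wording and a validity flag for each reading. Exact PD sample times are already entered in the eCRF (Protocol 7.2.3.2.1). The start time of an i.v. inhibitor needs attention: Protocol 5.2.2 asks for clock times only for oral P2Y₁₂ antagonists, so it would have to come from the deviation record or source notes. The existing 30-minute row already depends on the same information. The downside is that the two PPS analyses may have different denominators, which should be reported. No clinical rule changes.
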